Investigational Drug Durvalumab (MEDI4736) and
tremelimumab

Study Number ESR-16-12034

Version Number 11

Date 5 October 2018

A Pilot Pre-Surgical Study Evaluating Anti-PD-L1 Antibody (Durvalumab [MEDI4736]) Plus Anti-CTLA-4 Antibody (Tremelimumab) in Patients with Hormone Receptor Positive, HER2 Negative Breast Cancer

Sponsor: The University of Texas MD Anderson Cancer Center

PROTOCOL SYNOPSIS

Clinical Protocol 2016-0902 IND 134400

Study Title: A Pilot Pre-Surgical Study Evaluating Anti-PD-L1 Antibody (Durvalumab) Plus Anti-CTLA-4 Antibody (Tremelimumab) in Patients with Hormone Receptor Positive, HER2 Negative Breast Cancer
Clinical Phase: Pilot
Study Duration: 24 months
Investigational Product(s) and Reference Therapy: Durvalumab will be supplied in glass vials containing 500 mg of liquid solution at a concentration of 50 mg/mL for intravenous (IV) administration. Tremelimumab is supplied as a sterile solution for IV infusion, filled in 20 mL clear glass vials with a rubber stopper and aluminum seal. Each vial contains 20 mg/mL (with a nominal fill of 20 mL, accounting to 400 mg/vial) of tremelimumab, in an isotonic solution at pH 5.5.
Research Hypothesis Our hypotheses are: 1) that it will be feasible to enroll patients with hormone receptor (HR)-positive, HER2-negative breast cancer onto a trial evaluating anti-CTLA-4 (cytotoxic T-lymphocyte-associated antigen-4) therapy (tremelimumab) plus anti-PD-L1 (programmed cell death ligand 1) therapy (durvalumab) prior to initiating standard neoadjuvant chemotherapy, 2) that the combination of tremelimumab plus durvalumab therapy will have an acceptable safety profile in HR+/HER2- breast cancer patients; and 3) that tremelimumab plus durvalumab therapy will lead to measurable immunologic changes, with identification of novel biomarkers that can be used for immune monitoring and clinical correlation in the setting of HR+/HER2- breast cancer.
Objectives: Primary Objectives: 
• To evaluate the feasibility of enrolling patients with HR+/HER2- breast cancer onto a trial evaluating investigational agents prior to initiating standard neoadjuvant chemotherapy.• To evaluate the safety and tolerability of tremelimumab plus durvalumab in patients with HR+/HER2- breast cancer.

Secondary Objective(s):

To assess immunologic/molecular responses to tremelimumab and durvalumab in patients with HR+/HER2- breast cancer who receive the combination therapy.

Exploratory Objective(s):

To evaluate the pathologic response in patients with HR+/HER2- breast cancer receiving tremelimumab plus durvalumab prior to initiating standard neoadjuvant chemotherapy.

Study Design:

Open-label, single-arm, presurgical pilot study in patients with HR+/HER2- breast cancer

Number of Centers: 1**Number of Subjects: 15****Study Population:**

Breast cancer patients with HR+/HER2- disease planned to receive neoadjuvant chemotherapy

Inclusion Criteria:

For inclusion in the study, patients should fulfill the following criteria:

- Written informed consent and any locally-required authorization (e.g., HIPAA) obtained from the subject prior to performing any protocol-related procedures, including screening evaluations
- Age ≥ 18 years at time of study entry
- Eastern Cooperative Oncology Group (ECOG) performance status of 0 or 1
- Hormone receptor positive (defined as estrogen receptor [ER] and/or progesterone receptor [PR] positive), HER2 negative breast cancer that is clinically staged II-III with no known metastatic disease. ER and/or PR defined as positive if expression $>10\%$ by immunohistochemistry (IHC). HER2 negative or non-amplified as determined by the current ASCO-CAP criteria which are as follows: HER2 testing by IHC as 0 or 1+. If HER2 is 2+, ISH (in situ hybridization) must be performed. HER2 is positive if:
 - IHC 3+ based on circumferential membrane staining that is
 - complete, intense
 - ISH positive based on:
 - Single-probe average HER2 copy number ≥ 6.0 signals/cell.
 - Dual-probe HER2/CEP17 ratio ≥ 2.0 ;c,e with an average HER2 copy number ≥ 4.0 signals/cell
 - Dual-probe HER2/CEP17 ratio ≥ 2.0 ;c,e with an average HER2 copy number < 4.0 signals/cell
 - Dual-probe HER2/CEP17 ratio < 2.0 ;c,e with an average HER2 copy number ≥ 6.0 signals/cell
- Chemotherapy is planned for the patient in the neoadjuvant setting
- Adequate normal organ and marrow function as defined below:
 - Hemoglobin ≥ 9.0 g/dL
 - Absolute neutrophil count (ANC) $\geq 1.5 \times 10^9/L$ (≥ 1500 per mm^3)
 - Platelet count $\geq 100 \times 10^9/L$ ($\geq 100,000$ per mm^3)
- Serum bilirubin ≤ 1.5 x institutional upper limit of normal (ULN). This will not apply to subjects with confirmed Gilbert's syndrome (persistent or recurrent hyperbilirubinemia that is predominantly unconjugated in the absence of hemolysis or hepatic pathology), who will

be allowed only in consultation with their physician, Principal Investigators (PI) or co-PIs approval

- AST (SGOT)/ALT (SGPT) ≤ 2.5 x institutional upper limit of normal unless liver metastases are present, in which case it must be ≤ 5 x ULN
- Creatinine CL >40 mL/min by the Cockcroft-Gault formula (Cockcroft and Gault 1976) or by 24-hour urine collection for determination of creatinine clearance:

Males:

$$\text{Creatinine CL (mL/min)} = \frac{\text{Weight (kg)} \times (140 - \text{Age})}{72 \times \text{serum creatinine (mg/dL)}}$$

Females:

$$\text{Creatinine CL (mL/min)} = \frac{\text{Weight (kg)} \times (140 - \text{Age}) \times 0.85}{72 \times \text{serum creatinine (mg/dL)}}$$

- Female subjects must either be of non-reproductive potential (ie, post-menopausal by history: ≥ 60 years old and no menses for ≥ 1 year without an alternative medical cause; OR history of hysterectomy, OR history of bilateral tubal ligation, OR history of bilateral oophorectomy) or must have a negative urine pregnancy test upon study entry.
- Subject is willing and able to comply with the protocol for the duration of the study including undergoing treatment and scheduled visits and examinations including follow up.

Exclusion Criteria:

Patients should not enter the study if any of the following exclusion criteria are fulfilled:

- Involvement in the planning and/or conduct of the study (applies to both AstraZeneca staff and/or staff at the study site)
- Participation in another clinical study with an investigational product during the last 1 month prior to initiation of therapy
- Any previous treatment with a PD1 or PD-L1 inhibitor, including durvalumab or an anti-CTLA4, including tremelimumab
- History of another primary malignancy except for:
 - Malignancy treated with curative intent and with no known active disease ≥ 5 years before the first dose of study drug and of low potential risk for recurrence
 - Adequately treated non-melanoma skin cancer or lentigo maligna without evidence of disease
 - Adequately treated carcinoma in situ without evidence of disease eg, cervical cancer in situ
- Has received therapy for this current diagnosis of breast cancer including endocrine therapy or chemotherapy.
- A single QT interval corrected for heart rate (QTc) ≥ 470 ms. If an ECG is interpreted to be a prolonged QT interval, 2 additional ECGs will be obtained. The PI will then evaluate all three ECGs and determine whether the patient should be excluded. Mean QT interval corrected for heart rate (QTc) ≥ 470 ms calculated from 3 electrocardiograms (ECGs) using Fredericia's Correction
- Current or prior use of immunosuppressive medication within 28 days before the first dose of durvalumab or tremelimumab, with the exceptions of intranasal and inhaled corticosteroids or systemic corticosteroids at physiological doses, which are not to exceed 10 mg/day of prednisone, or an equivalent corticosteroid
- Active or prior documented autoimmune disease within the past 2 years NOTE: Subjects with vitiligo, Grave's disease, or psoriasis not requiring systemic treatment (within the past 2 years) are not excluded.

- Active or prior documented inflammatory bowel disease (e.g., Crohn's disease, ulcerative colitis)
- History of primary immunodeficiency
- History of allogeneic organ transplant
- History of hypersensitivity to durvalumab or tremelimumab or any excipient
- History of hypersensitivity to the combination or comparator agent (if applicable)
- Uncontrolled intercurrent illness including, but not limited to, ongoing or active infection, symptomatic congestive heart failure, uncontrolled hypertension, unstable angina pectoris, cardiac arrhythmia, active peptic ulcer disease or gastritis, active bleeding diatheses including any subject known to have evidence of acute or chronic hepatitis B, hepatitis C or human immunodeficiency virus (HIV), or psychiatric illness/social situations that would limit compliance with study requirements or compromise the ability of the subject to give written informed consent
- Known history of previous clinical diagnosis of tuberculosis
- History of leptomeningeal carcinomatosis
- Receipt of live attenuated vaccination within 30 days prior to study entry or within 30 days of receiving durvalumab or tremelimumab
- Female subjects who are pregnant, breast-feeding or male or female patients of reproductive potential who are not employing an effective method of birth control
- Any condition that, in the opinion of the investigator, would interfere with evaluation of study treatment or interpretation of patient safety or study results
- Subjects with uncontrolled seizures.

Investigational Product(s), Dose, and Mode of Administration:

Durvalumab, 1500 mg Q4W (equivalent to 20 mg/kg Q4W) for 2 doses/cycles in patients ≥ 30 kg
Tremelimumab 75 mg Q4W (equivalent to 1 mg/kg Q4W) for 2 doses/cycles in patients ≥ 30 kg
Weight-based dosing should be utilized for patients <30 kg durvalumab 20 mg/kg Q4 and tremelimumab 1 mg/kg Q4

Study Assessments and Criteria for Evaluation:

The study's primary endpoints are to evaluate the feasibility of enrolling patients with HR+/HER2- breast cancer onto a trial evaluating investigational agents prior to initiating standard neoadjuvant chemotherapy and to evaluate the safety and tolerability of tremelimumab plus durvalumab in patients with HR+/HER2- breast cancer.

Feasibility Assessments:

Feasibility will be measured by 2 achievements. If both are met, then upfront treatment with tremelimumab plus durvalumab will be feasible for future trials in HR+/HER2- breast cancer patients. The 2 measures are:

- Patients are willing to enroll. This will be established if we can enroll all 15 patients within 12 months of starting the study.
- Patients can complete the protocol. If at least 10 patients complete the study and have available immune data, the trial meets this feasibility criterion.

Safety Assessments:

All patients who receive at least one dose of study drug will be included in the safety monitoring and safety analysis. For trial monitoring and decisions about future trials, a patient will be determined to have an extreme toxicity (ETOX) if either condition is met:

- The patient experiences any grade 3 or higher adverse event (AE) that is possibly, probably, or definitely related to therapy received on this protocol and occurs up to 90 days after the last dose of therapy (durvalumab + tremelimumab). As an exception, any such AE that is potentially treatable with steroids will only count as an ETOX if it does not improve to grade 1 or better within 2 weeks.
- The patient has a delay in surgery of 6 weeks or more due to AE, even if that AE does not meet the definition of ETOX

Statistical Methods and Data Analysis:

Feasibility will be assessed according to the endpoint definition provided above. Since it is not known whether durvalumab plus tremelimumab can be safely used in the presurgical setting in patients with HR+, HER2- breast cancer, our other primary endpoint is safety. Adverse events will be tabulated by CTCAE grade and ETOX status. Surgery delay will be reported with the numbers of patients with any delay, as well as the median, IQR, min and max for delay times. If 6 or more patients experience ETOX, then this combination will be determined to be too toxic for these patients.

For blood and tumor measures, descriptive statistics including plots, tabulations, mean, median and standard deviations will be used to summarize data. Differences and/or percent changes will be calculated between pre- and post-therapy samples from each patient and described as continuous measures.

Sample Size Determination:

The selection of 15 patients for this pilot trial is to provide preliminary information for feasibility and safety, as well as to have at least 10 patients with full immune measures pre and post treatment for hypothesis generation and testing in the next trial. An accrual rate of 2 patients per month is anticipated. A maximum sample size of 15 patients will be enrolled. No hypotheses will be formally tested, but with 15 patients we can determine whether an unreasonable proportion of patients have high grade toxicities and gather estimates of immune and molecular changes in tumor and peripheral blood. These measures will be used to design a larger, hypothesis-driven trial.

SCHEDULE OF STUDY ASSESSMENTS

Study Week		1	2	3	4	5	6	7	8	Prior to Neoadjuvant Therapy	Surgery
Study Cycle		1				2					
Cycle Day	-28 to 0	1	8	15	28	1	8	15	28	Within 28 days	Within 56 days of completing neoadjuvant therapy
Informed Consent	X										
Demographics	X										
Medical History	X										
General Physical ¹	X	X ²				X				X	
Height, Weight ³	X										
Vital signs	X	X ⁴				X ⁴				X	
Performance Status (ECOG)	X	X ²				X				X	
Baseline Symptoms/Toxicity review	X	X ²				X				X	
Review of concomitant medications	X	X ²				X					
CBC	X	X ⁷				X					
aPTT and INR ⁵	X										
Chemistries ⁶	X	X ⁷				X				X	
TSH, free T4, free T3 ⁸	X	X ⁷				X				X	
HBsAg, Anti HCV, HIV antibody, Hepatitis A antibody	X										
Creatinine clearance	X										
Pregnancy Test (urine) ⁹	X										
Urinalysis ¹⁰	X	X				X					
Mammogram	X										
Breast Ultrasound ¹¹	X									X	
12-lead ECG ¹²	X	X									
Core Biopsy	X ¹³									X	
Surgical Specimen											X

Blood for PBMCs	X									X	X
Serum	X									X	X
Durvalumab		X				X					
Tremelimumab		X				X					
Gamma glutamyltransferase	X	X ⁷									

1. Full physical examination at baseline; targeted physical examination at other time points
2. If completed within 7 days of the date of treatment initiation, these do not need to be repeated.
3. Height only needs to be measured and recorded at the baseline assessment.
4. Subjects will have their blood pressure and pulse measured before, during, and after the infusion at the following times (based on a 60-minute infusion):
 - a. At the beginning of the infusion (at 0 minutes)
 - b. At 30 minutes during the infusion (± 10 minutes)
 - c. At the end of the infusion (60 minutes ± 10 minutes)
 - d. In the 1 hour observation period post-infusion: 30 and 60 minutes after the infusion (i.e. 90 and 120 minutes from the start of the infusion) (± 10 minutes) – for the first infusion only and then for subsequent infusions as clinically indicated
 - e. If the infusion lasts longer than 60 minutes, then blood pressure and pulse measurements should follow the principles as described above or more frequently if clinically indicated.
5. Coagulation tests: prothrombin time, APTT and INR – only performed at Screening and as clinically indicated.
6. Chemistries include: albumin, alkaline phosphatase, ALT, AST, amylase, lipase, calcium, bicarbonate, chloride, creatinine, glucose, LDH, magnesium, potassium, sodium, total bilirubin, total protein, BUN, uric acid. If total bilirubin is $\geq 2x$ ULN (and no evidence of Gilbert's syndrome), then bilirubin should be fractionated into direct and indirect bilirubin.
7. If screening laboratory assessments are performed within 3 days prior to Day 1 they do not need to be repeated at Day 1. Results for safety bloods must be available and reviewed before commencing an infusion. Gamma glutamyltransferase tested at Screening, Day 1 and as clinically indicated.
8. Free T3 and free T4 will only be measured if TSH is abnormal. They should also be measured if there is clinical suspicion of an adverse event related to the endocrine system.
9. Pre-menopausal female subjects of childbearing potential only

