6.2 Dosage and Administration

Patients will receive 1500 mg durvalumab via IV infusion q4w +/- 3 days for 2 doses/cycles and 75 mg tremelimumab via IV infusion q4w +/- 3 days for 2 doses/cycles. Dosing outside the window should be discussed with [name] and/or [name]. Tremelimumab will be administered first. Durvalumab infusion will start approximately 1 hour after the end of tremelimumab infusion. The duration will be approximately 1 hour for each infusion. A 1-hour observation period is required after the first infusion of durvalumab and tremelimumab. If no clinically significant infusion reactions are observed during or after the first cycle, subsequent infusion observation periods can be at the Investigator's discretion (suggested 30 minutes after each durvalumab and tremelimumab infusion).

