7. RESTRICTIONS DURING THE STUDY AND CONCOMITANT TREATMENT(S)

7.1 Restrictions during the study

The following restrictions apply while the patient is receiving study treatment and for the specific times before and after:

– Females of childbearing potential who are sexually active with a non-sterilized male partner must use at least 1 **highly** effective method of contraception (Table 3) from the time of screening and must agree to continue using such precautions for 180 days after the last dose of durvalumab + tremelimumab combination therapy. Non-sterilized male partners of a female patient must use male condom plus spermicide throughout this period. Cessation of birth control after this point should be discussed with a responsible physician. Not engaging in sexual activity for the total duration of the drug treatment and the drug washout period is an acceptable practice; however, periodic abstinence, the rhythm method, and the withdrawal method are not acceptable methods of birth control. Female patients should also refrain from breastfeeding throughout this period.

N.B Females of childbearing potential are defined as those who are not surgically sterile (ie, bilateral tubal ligation, bilateral oophorectomy, or complete hysterectomy) or post-menopausal.

Women will be considered post-menopausal if they have been amenorrheic for 12 months without an alternative medical cause. The following age-specific requirements apply:

- Women <50 years of age would be considered post-menopausal if they have been amenorrheic for 12 months or more following cessation of exogenous hormonal treatments and if they have luteinizing hormone and follicle-stimulating hormone levels in the post-menopausal range for the institution or underwent surgical sterilization (bilateral oophorectomy or hysterectomy).
- Women \geq 50 years of age would be considered post-menopausal if they have been amenorrheic for 12 months or more following cessation of all exogenous hormonal treatments, had radiation-induced menopause with last menses >1 year ago, had

chemotherapy-induced menopause with last menses >1 year ago, or underwent surgical sterilization (bilateral oophorectomy, bilateral salpingectomy or hysterectomy).

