Highly effective methods of contraception, defined as one that results in a low failure rate (ie, less than 1% per year) when used consistently and correctly are described in Table 3. Note that some contraception methods are not considered highly effective (e.g. male or female condom with or without spermicide; female cap, diaphragm, or sponge with or without spermicide; non-copper containing intrauterine device; progestogen-only oral hormonal contraceptive pills where inhibition of ovulation is not the primary mode of action [excluding Cerazette/desogestrel which is considered highly effective]; and triphasic combined oral contraceptive pills).

Table 3 Highly Effective methods of contraception (<1% failure rate)

Barrier/Intrauterine methods	Hormonal Methods

 • Copper T intrauterine device • Levonorgestrel-releasing intrauterine system (eg, Mirena®)^a 	
 • Etonogestrel implants: e.g. Implanon or Norplan • Intravaginal device: e.g. ethinylestradiol and etonogestrel • Medroxyprogesterone injection: e.g. Depo-Provera • Normal and low dose combined oral contraceptive pill • Norelgestromin/ethinylestradiol transdermal system • Cerazette (desogestrel)

^a This is also considered a hormonal method

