8. STUDY PROCEDURES

8.1 Schedule of study procedures

Before study entry, throughout the study, and following study drug discontinuation, various clinical and diagnostic laboratory evaluations are outlined. The purpose of obtaining these detailed measurements is to ensure adequate safety and tolerability assessments. Clinical evaluations and laboratory studies may be repeated more frequently if clinically indicated.

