8.1.1 Screening Phase

Screening procedures will be performed up to 28 days before Day 1, unless otherwise specified. All subjects must first read, understand, and sign the IRB -approved ICF before any study-specific screening procedures are performed. After signing the ICF, completing all screening procedures, and being deemed eligible for entry, subjects will be enrolled in the study. Procedures that are performed prior to the signing of the ICF and are considered standard of care may be used as screening assessments if they fall within the 28-day screening window. Refer to the Study Calendar for complete list of all the procedures that will be performed during the Screening Visit.

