8.1.2 Treatment Phase

Procedures to be conducted during the treatment phase of the study are presented in the Schedule of Assessments. Screening procedures performed within 7 days of Cycle 1 Day 1 (C1D1) do not need to be repeated on C1D1.

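### The only scheduled pregnancy test is at screening, so it can be 28 days old at the first infusion and 59 days old at the second

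*Combined protocol and SAP*

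**What the plan says.** In the Schedule of Study Assessments the urine pregnancy test row is marked once, under Day -28 to 0. It is blank at Cycle 1 Day 1, at Cycle 2 Day 1 and before neoadjuvant therapy. Footnote 9 restricts it to "Pre-menopausal female subjects of childbearing potential only". Section 8.2.5 names urine hCG and leaves its timing to the schedule. Inclusion criterion 7 asks for a negative urine test at study entry but sets no interval to the first dose.

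Four other provisions bear on timing:

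- Section 8.1.1: "Screening procedures will be performed up to 28 days before Day 1, unless otherwise specified".
- Section 6.2: "Patients will receive 1500 mg durvalumab via IV infusion q4w +/- 3 days for 2 doses/cycles", with the same window for tremelimumab.
- Section 8.1.2: "Screening procedures performed within 7 days of Cycle 1 Day 1 (C1D1) do not need to be repeated on C1D1".
- Section 8.1: "Clinical evaluations and laboratory studies may be repeated more frequently if clinically indicated".

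Section 7.1 requires sexually active women of childbearing potential with a non-sterilized partner to use at least one highly effective contraceptive method "from the time of screening and must agree to continue using such precautions for 180 days after the last dose". The partner must also use a condom with spermicide. A highly effective method is one with "a low failure rate (ie, less than 1% per year) when used consistently and correctly".

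Pregnancy is an exclusion (section 4.2, item 18), ends study treatment (section 4.3, item 4) and requires immediate discontinuation of both drugs (section 10.3.3.4).

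**The concern.** The rules that keep a pregnant patient from being dosed work only if the pregnancy is known on the day. The schedule orders blood counts, chemistries, TSH and urinalysis at both infusions, but no pregnancy test at either. Two kinds of pregnancy could pass unnoticed: one from contraceptive failure after screening, and one conceived too shortly before screening for the urine test to be positive. The contraception requirement lowers the chance of the first but does not detect it. Because it starts at screening, it does nothing about the second.

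At stake is fetal exposure to one or both infusions, which cannot be undone once given; section 1.1.3 gives tremelimumab a terminal half-life of 22 days. No endpoint, stopping boundary or analysis is affected. This is a point about participant safety.

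**Working it through.** The plan states no maximum age for the pregnancy test, so there is no figure of its own to reproduce.

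**Inputs**

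- Screening window: 0 to 28 days before Day 1 (section 8.1.1).
- Interval between doses: 28 ± 3 days, that is 25 to 31 days (section 6.2).
- Scheduled tests after screening: none.
- Contraceptive failure: at most 1% per year with correct use (section 7.1).
- Patients: 15. The number of childbearing potential is not given.

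**Age of the test at each dose**

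- Dose 1: 0 to 28 days.
- Dose 2, minimum: 0 + 28 - 3 = 25 days.
- Dose 2, maximum: 28 + 28 + 3 = 59 days.

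If the column heading is taken literally, with a Day 0 before Day 1, the maxima become 29 and 60 days. All of these are limits within the protocol windows. Appendix 1 lets a Grade 2 event hold drug until a steroid taper of 28 days or more is complete, so a held second dose could fall later still.

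**Does another clause close the gap?**

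- Section 8.1.2 might be read as requiring a repeat of any screening procedure more than 7 days old. The same section refers to the schedule for what is done during treatment, and the schedule has no pregnancy test at Cycle 1 Day 1. If the favourable reading is granted, the age is 0 to 7 days at dose 1 and 25 to 7 + 28 + 3 = 38 days at dose 2. No test is scheduled at dose 2 on any reading.
- Section 8.1 permits extra tests at the clinician's discretion. It orders none.
- Urine is collected at Cycle 1 Day 1 and Cycle 2 Day 1, but the urinalysis panel in Table 7 does not include hCG.
- Footnote 7 requires safety bloods to be reviewed before infusion. The pregnancy test is a urine test and its row does not carry that footnote.

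**Size of the contraceptive-failure risk over 59 days**

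Probability per woman = annual rate × 59/365. Expected pregnancies = that probability × number of women who could conceive.

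| Annual failure rate | Per woman | 15 women | 5 women (assumption) |
|---|---|---|---|
| 1% (protocol ceiling) | 0.01 × 59/365 = 0.0016 | 0.024 | 0.008 |
| 10% (assumed, inconsistent use) | 0.10 × 59/365 = 0.0162 | 0.24 | 0.08 |

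The compound formula, 1 - (1 - 0.01)^(59/365), also gives 0.0016. The chance of at least one conception at the 1% rate is then about 0.8%, 1.6% or 2.4% if 5, 10 or 15 patients could conceive. Conceptions before screening come on top of this and cannot be quantified from the documents.

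**The case against.** The strongest reply is that the absolute risk is very small and the benefit of extra testing smaller still. At 1% per year, a test at dose 1 could catch at most 0.01 × 28/365 × 15 = 0.0115 contraceptive failures, and a test at dose 2 at most 0.01 × 31/365 × 15 = 0.013 conceived after dose 1. With a 22-day half-life, the latter would already have been exposed to tremelimumab from dose 1 and would be spared only the second infusion. A dosing-day test can also miss a very recent conception, just as the screening test can. The partner's condom and spermicide should push the true rate below 1%, and the 10% rate has no source in the documents. All of this stands. It limits how serious the point is, but not whether the gap exists.

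A second reply is that a negative test at study entry could be read as a test close to the first dose. That reading is possible, but the criterion gives no number of days and leaves dose 2 untested.

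A third is that physical examination, symptom review and medication review are scheduled on both dosing days (those at Cycle 1 Day 1 may be skipped if done within the previous 7 days), and a missed period or stopped contraception could come to light there. It could, but none of these contacts orders a test.

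**Conclusion.** The point holds. Within protocol windows the only scheduled pregnancy test can be 28 days old at the first infusion and 59 days old at the second. The reading of section 8.1.2 most favourable to the plan reduces these to 7 and 38 days and still leaves dose 2 without a test.

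The risk is low: about 0.16% per woman over 59 days at the protocol's ceiling failure rate, or 0.024 expected pregnancies if all 15 patients could conceive. Under the assumed 10% rate it would be ten times that. These figures cover contraceptive failure only and depend on an unknown number of women of childbearing potential.

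The change should be made because the exposure cannot be reversed, the protocol's own pregnancy rules depend on detection, and the cost is close to nil. It is not a defect that threatens the trial's conclusions.

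**What to change.** For women of childbearing potential, add a urine pregnancy test to two columns of the Schedule of Study Assessments:

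- Cycle 1 Day 1, waived if a test was done within the previous 3 days, matching the laboratory waiver in footnote 7.
- Cycle 2 Day 1, with no waiver.

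Run each test on the urine already collected for urinalysis and read it before the infusion starts. The test is then at most 3 days old at dose 1 and same-day at dose 2.

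The cost is at most 2 × 15 = 30 inexpensive urine tests, with no extra visit or sample, and one amendment to the schedule.

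The same amendment can tidy a wording mismatch that carries no safety weight. Inclusion criterion 7 makes a negative test a condition of entry for post-menopausal women under 60 without the listed surgery, whereas footnote 9 and section 8.2.5 do not order one for them. As written, staff who follow the schedule could create an eligibility deviation. Either widen footnote 9 to match the criterion, or bring the criterion into line with the menopausal definitions in section 7.1.
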